TheraDrive is a low-cost robotic system for post-stroke upper extremity rehabilitation. The system uses off-the-shelf computer gaming wheels with force feedback to help reduce motor impairment and improve function in the arms of stroke survivors. Preliminary results from various studies have shown that the original TheraDrive system lacked a robust mechanical linkage which could withstand the forces exerted by patients, lacked a patient-specific adaptive controller to deliver personalized therapy, and was not capable of delivering effective therapy to severely low-functioning patients. A new low-cost, high-force haptic robot with a single degree of freedom has been developed to address these concerns. This study has two purposes: first, to test the viability and usability of the new robot system alongside the original TheraDrive system; and second, to test if low-functioning patients benefit, and if so how much, from using force-feedback therapy as opposed to devices with zero impedance. This will be done by recruiting approximately 36 human subjects. Exercises will be performed by study subjects and an adaptive controller will monitor patient performance to ensure that exercises are difficult but doable, which is important for maintaining patient motivation. We hypothesize that not only will the new system be viable, but that it will provide better robot-assisted therapy to a large variety of patients, especially low-functioning stroke survivors with hemiplegia.

Objectives

Overall objectives

This study is being performed to assess the usability of affordable force-feedback devices for stroke rehabilitation. For this pilot study, subjects will use two or more devices (a commercial force-feedback

joystick, commercial force-feedback wheel, and a custom force-feedback device) to complete games and exercise tasks to determine the ease of using these devices and their impact on motor performance and function. The long-term goal of this project is to develop an inexpensive high-force haptic rehabilitation robot that can safely be used by patients at home without therapist supervision. A sub-goal was to simulate the human-machine interaction. We will use our assessment tools to determine upper arm kinematic and dynamic workspace recovery

Primary outcome variable(s)

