Part A Usability Study: Cross-sectional study comparing outcome variables for stroke survivors with varying levels of motor deficit impairment in their upper extremity. Subjects with mild motor deficits will be compared against stroke survivors with severe motor deficits after completing exercises with both commercial and custom therapy devices. Therapy exercises will be performed in random order, decided prior to the session. It will be randomly determined which robot the patient will use first, the order of operating modes used for the new robot, and the order of therapy exercises performed in each mode. Surface Electromyography (EMG) will be used in order to detect the small electric currents, or signals, which are generated by muscle activity. The collection of the strength and pattern of the signals will permit us to verify muscle activity over time. Part B Therapy Study: Pre-post study looking at change in outcome variables over 12 therapy sessions (three times a week for one month). Only low and mid functioning stroke survivors will be asked to participate in Part B of the study, and only the custom haptic device will be used by the study subjects. Pre-post evaluations will be administered at session 1 and 12. Surface Electromyography (EMG) will be used in order to detect the small electric currents, or

signals, which are generated by muscle activity. The collection of the strength and pattern of the signals will permit us to verify muscle activity over time.

Study duration

1) We estimate that it will take 3 years from the date of IRB approval to enroll all subjects and complete the study. 2) Part A - The subject's participation in the study will be limited to approximately 4 hours; 1-2 hours to be evaluated by a therapist with expertise in stroke rehabilitation and 2-3 hours of assessing the viability and usability of the various therapy devices. Part B - Subjects enrolled in Part B will be asked to return 3 times a week for 1 month (12 sessions). All sessions will last approximately 1.5 hours. 3) Projected date of the proposed study: 3/1/14 to 7/1/17.

Resources necessary for human research protection

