
Subjects will be given a 15 minute break. 4) First Therapy Device: Subjects will be introduced to several robots: a wheel, joystick, and custom crank chosen randomly (like the flip of a coin). First, they will be trained in the use of all robots and their safety features. Following training, they will be asked to move each robot into different positions, first without pressure applied to the handle, and then with pressure applied to the handle. After each exercise they will be asked about their level of exercise and level of pain discomfort. After subjects finish all exercises with a robot, they will be given a survey about the robot. They will also be given surveys to discuss their experience with the device and their level of motivation for use of them. The surface EMG may be utilized during the entirety of the participant's interaction with the novel therapy device. Prior to its placement on the subject, the reason for its use will be thoroughly explained. 5) Break: Subjects will be given a 15 minute break. 6) Subsequent Therapy Device: Subjects will be instructed in the use of another robot. The same procedure will be followed as in the first evaluation. The surface EMG may be utilized during the entirety of the participant's interaction with the novel therapy device. Prior to its placement on the subject, the reason for its use will be thoroughly explained. 7) Final Survey: Subjects will be given a survey asking them to evaluate the robots and indicate which robot they prefer. Part B: For subjects invited to participate in Part B of the study - only low functioning stroke survivors are eligible - participation in this part of the study will include the following steps: 1) Informed Consent: After arrival, subjects will review and sign the consent form with study personnel present. 2a) Pre-Assessments: If subjects are only participating in Part B of the study, at their first visit, a member of the research team will evaluate their affected arm and assess their ability to use it. Subjects will be evaluated using a battery of assessments in order to determine their level of impairment such as the Beck Depression Inventory, Upper Extremity Fugl-Meyer, Montreal Cognitive Assessment, Jebson Taylor, Box in Block, Modified Ashworth, and grip strength using a dynamometer, etc. If a study subject participated in Part A, they will not be reevaluated by a therapist. 2b) Workspace Assessment: Same as in Part A 2) Custom Therapy Device: Subjects will be introduced to the custom robot. They will be trained in the use of this robot and its safety features (1st session). Following training, they will be asked to move the robot into different positions. After each exercise subjects will be asked about their level of exercise and level of pain discomfort. Subjects will continue to work with the custom therapy device for 12 sessions over the course of one month. The surface EMG may be utilized during the entirety of the participant's interaction with the novel therapy device. Prior to its placement on the subject, the reason for its use will be thoroughly explained. 3) Motivation Questionnaire: At the end of their 1st and 12th sessions, subjects will be asked to complete a questionnaire assessing their level of motivation. 4) Post-Study Survey: After their last session, subjects will be asked to complete a survey assessing the robot. 5) Post-Study Assessment: After their last session, a certified therapist will evaluate the participants' affected arm and assess their ability to use it. In addition, they will also be evaluated for depression and a mental health assessment will be given.

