
The following documents are currently attached to this item:

There are no documents attached for this item.

Deception

Does your project use deception?

No

Analysis Plan

1) Clinical data will be analyzed to determine how subjects low versus high function perform on metrics developed using the robots. 2) Trajectory tracking using a baseline with zero resistance will be established for each patient. The root mean square metric will be used to assess accuracy in tracking tasks and subjects' performance across groups (low versus high) and devices in Part A, and across time in Part B. Using a 2-way ANOVA test for Part A, and an alpha of 0.05, significant difference across groups will be detected. A paired t-test, and an alpha of 0.05, will detect significant difference across time pre-post the 12 sessions. 3) Data collected from the surface EMG will be analyzed to verify muscle activity over time. 4) Data results will be used to build a simulation model of the human-robot tracking and determine a prediction of the joint and muscle forces that are used in Part A and Part B. 5) Data collected with the kinect will be assessed for kinematic and dynamic workspace. The data will be fitted to a computerized model of the upper limb to extract forces and positions defining dynamic and kinematic workspace.

The following documents are currently attached to this item:

There are no documents attached for this item.

Are you conducting research outside of the United States?

No

Data confidentiality

x Paper-based records will be kept in a secure location and only be accessible to personnel involved in the study.

x Computer-based files will only be made available to personnel involved in the study through the use of access privileges and passwords.

Prior to access to any study-related information, personnel will be required to sign statements agreeing to protect the security and confidentiality of identifiable information.

x Wherever feasible, identifiers will be removed from study-related information.

A Certificate of Confidentiality will be obtained, because the research could place the subject at risk of criminal or civil liability or cause damage to the subject's financial standing, employability, or liability.

A waiver of documentation of consent is being requested, because the only link between the subject and the study would be the consent document and the primary risk is a breach of confidentiality. (This is not an option for FDA-regulated research.)

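### Part A's two-way ANOVA names no subject term although each subject uses several devices; with a pooled residual and positively correlated scores, the group test exceeds its stated 0.05

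*Combined protocol and SAP*

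**What the plan says.** Item 2 of the Analysis Plan uses root-mean-square (RMS) tracking error to assess accuracy and "performance across groups (low versus high) and devices in Part A". The method follows: "Using a 2-way ANOVA test for Part A, and an alpha of 0.05, significant difference across groups will be detected". For Part B the same item names a paired t-test.

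Device is a within-subject factor. Under Overall objectives, "subjects will use two or more devices". In Procedures, Part A, step 4, "Subjects will be introduced to several robots: a wheel, joystick, and custom crank", and in step 6, "Subjects will be instructed in the use of another robot". Low or high function is a property of the person, so group is a between-subject factor.

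Two further statements bear on what enters the model. The Analysis Plan says: "Trajectory tracking using a baseline with zero resistance will be established for each patient". It does not say whether that baseline is subtracted, used as a covariate, or only described. Study Design, Part A, randomises "the order of operating modes used for the new robot, and the order of therapy exercises performed in each mode", and Procedures, step 4, has several exercises on each robot ("After subjects finish all exercises with a robot, they will be given a survey about the robot"). So a subject can yield several RMS values per device, and the new robot is run in more than one mode.

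Nowhere do the documents give a subject effect, a repeated factor, an error term, or the number of RMS values per subject and device. The Analysis Plan states that no document is attached to it.

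**The concern.** A two-way ANOVA in its ordinary form treats all rows as independent and tests every effect against one residual. Here the rows come in sets of two or three from the same impaired arm. If those rows are positively correlated, the group contrast has more variance than the pooled residual credits it with, and the device contrast has less. The group p-value is then too small. With one value per device, the device p-value is too large.

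The group difference is the one result that the plan promises from this test. The device comparison bears on the first purpose in the Abstract, which sets the new robot beside the original system.

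**Working it through.** **Inputs from the documents.** Nominal alpha is 0.05 (Analysis Plan, item 2). The number of devices per subject is k = 2 or 3 (Overall objectives; Procedures, Part A). The sample size is about 36 in the Abstract and 56 for Parts A and B together under Accrual. No Part A number or low/high split is given, and there is no power calculation, SD or correlation.

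**Assumptions.** 18 subjects per group, complete data, one RMS value per subject and device, total variance 1, and equal correlation ρ between any two devices within a subject, with ρ = 0, 0.1, 0.3, 0.5, 0.7. Zero is included because taking RMS relative to each patient's zero-resistance baseline could remove much of the subject effect.

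**Step 1: expected mean squares.** Group and between-subject mean squares have expectation 1 + (k−1)ρ under the null. Device and within-subject mean squares have expectation 1 − ρ. The pooled residual combines 34 between-subject and 34(k−1) within-subject degrees of freedom, so its expectation is [1 + (k−1)ρ + (k−1)(1−ρ)]/k = 1 for any ρ.

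**Step 2: size of the pooled group test.** In large samples, size = 2 × [1 − Φ(1.96/√(1 + (k−1)ρ))].
- k = 2, ρ = 0.3: 1.96/√1.3 = 1.719, giving 0.086.
- k = 3, ρ = 0.5: 1.96/√2 = 1.386, giving 0.166.

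| ρ | 2 devices | 3 devices |
|---|---|---|
| 0 | 0.050 | 0.050 |
| 0.1 | 0.062 | 0.074 |
| 0.3 | 0.086 | 0.121 |
| 0.5 | 0.110 | 0.166 |
| 0.7 | 0.133 | 0.206 |

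Simulating the chi-square components (400,000 draws, 36 subjects) gives 0.050, 0.062, 0.085, 0.110, 0.133 and 0.049, 0.073, 0.120, 0.165, 0.205. Results at 20 and 56 subjects agree within about 0.003, so the unstated sample size hardly matters. At ρ = 0 the stated 0.05 is reproduced. Testing group against between-subject variation gives 0.049 to 0.051 throughout.

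**Step 3: size of the pooled device test, one value per device.** The device mean square is deflated by 1 − ρ. At ρ = 0.3 with two devices, 1.96/√0.7 = 2.343, giving 0.019 (simulated 0.020). With three devices, exp[−5.991/(2 × 0.7)] = 0.014 (simulated 0.015).

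**Step 4: several rows per device.** This rests on further assumptions: subject variance share 0.3, three devices, four rows each, and subject-by-device share 0, 0.1, 0.2, 0.3. The pooled device test then has size 0.014, 0.053, 0.105, 0.162, so its error can change direction. A random subject effect alone on the same rows gives 0.050, 0.131, 0.231, 0.329. Averaging to one value per subject and device gives 0.049 to 0.051.

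**The case against.** The strongest reply is that many authors would call a mixed design with two factors a two-way ANOVA, and that the paired t-test for Part B shows a team aware of within-subject data. A reader might infer from the wording that the plan has chosen an invalid test. The documents do not support that: they leave the model open, and the inflation needs both the pooled form and a positive correlation. Equally, the Part B wording does not settle Part A, where no repeated form is named.

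A second reply is that false positives matter little when the groups are defined by motor function and the outcome is a motor task. This largely stands. If the true difference were 1 SD (an assumption), the split-plot test would have about 95% power and the pooled test 97 to 99% (18 per group; ρ = 0.3 with two devices, 0.5 with three), so conclusions would seldom differ. Accrual justifies the sample size by this being a pilot, and no decision is tied to the p-value.

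Third, averaging all rows to one value per device would merge the new robot's operating modes. The Abstract's second purpose compares force feedback with zero impedance, so if the modes differ in impedance, that averaging could hide the contrast. This stands, and the fix allows for it.

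A reader might also infer that Part A as a whole is unreliable. The survey-based usability results do not pass through this test and are unaffected.

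**Conclusion.** The concern holds as an unspecified model with a conditional consequence. The plan does not state the error structure of a design with one between-subject and one within-subject factor. Under the pooled reading, any positive within-subject correlation puts the group test above its stated 0.05. For correlations of 0.1 to 0.7 the excess runs from about 0.01 to 0.08 with two devices and from about 0.02 to 0.16 with three. With one value per device, the device test is conservative.

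The correlation is assumed. A positive value is what one would expect of one arm on several devices, but the documents give none, and at zero there is no excess. The multi-row figures rest on further assumed variance shares and show only that the unit of analysis must be stated. The harm is miscalibrated reported p-values. The plan should be corrected because the correction is cheap, not because the study's conclusions are known to be at risk.

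**What to change.** In item 2 of the Analysis Plan, replace the two-way ANOVA with a split-plot (mixed) ANOVA or a linear mixed model for RMS error, with a random subject effect and fixed group, device and group-by-device effects. Test group against between-subject variation, and device and the interaction against the subject-by-device residual.

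State the unit of analysis: one RMS value per subject and device condition, averaged over exercises but not over the new robot's operating modes. Either make each mode its own level of the device-condition factor, or prespecify the one mode used for the device comparison. If exercise-level rows are kept, add a random subject-by-condition effect. State also how the zero-resistance baseline enters.

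With three or more conditions, use a Greenhouse-Geisser correction, or an unstructured covariance with a small-sample degrees-of-freedom method (Kenward-Roger). The latter also accommodates subjects who used only two devices. The method should be named: at 18 per group with three devices and complete data, an unstructured Wald test has size 0.069 by chi-square and 0.055 by F with unadjusted degrees of freedom. Kenward-Roger with incomplete data was not simulated here.

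The cost is a few sentences, with no new data, visits or subjects. The group p-value will usually be less favourable, but not always: at a correlation of 0.1 the split-plot p-value was the smaller one in about 25% (two devices) and 16% (three devices) of simulated null trials.
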